3.1. Sample Size

We calculated that 41 patients per group will be needed to detect a difference in the PASS score of 25 points with a within-group standard deviation of 40 points (9), 80 % power and a 2-sided alfa level of 0.05. Hence, the sample size is set at 45 patients per group to allow for possible dropouts.

3.2. Randomization and Blinding

The Hospital Pharmacy at Herlev Hospital, Denmark, will conduct randomization in random block sizes without stratification (block-randomization) using statistical software approved for

this purpose, e.g. from the website www.randomization.com. Dropouts (treatment with study medication less than 48 hours) will be replaced by new subjects, and a mirror-randomization will be performed.

Labelling will also be performed by the Hospital Pharmacy at Herlev Hospital, according to Annex 13 of the Good Manufacturing Practice guidelines of the International Conference on Harmonization-GCP guidelines and local law. The study medication will be delivered directly to the respective trial sites by the Hospital Pharmacy at Herlev Hospital in vials labelled with the randomization number corresponding to the allocation and the information that it is intended for use in a clinical trial only. Each vial contains 0.6 ml of transparent fluid corresponding to 12 mg methylnaltrexone or matching volume of Ringer's Lactate.

A list of randomization numbers is devised by the Hospital Pharmacy at Herlev Hospital and provided to trial personnel. After inclusion, a randomization number is assigned to the individual trial participant as instructed by the Hospital Pharmacy.

4. Study Population

4.1. Subject Disposition

Patients will be contacted by study personnel upon admission to be informed and potentially included in the study. Participation is complete voluntary, and consent can be revoked, should the participant wish to do so. Participants do not receive any economic compensation, but participation will be potentially beneficial for patients receiving active medication and it is expected that this study will produce important knowledge on the treatment of acute pancreatitis for future patients. Furthermore, all patients, regardless of whether they receive active treatment or placebo, may gain new insights and understanding into the pathophysiology of their disease and possible beneficial future treatment.

To identify patients at risk of moderate-to-severe disease, patients must fulfill two or more systemic inflammatory response syndrome (SIRS) criteria within the past 24 hours prior to inclusion. This assumption is based on previous findings that the fulfillment of two or more SIRS criteria is a good predictor of severity in patients with acute pancreatitis (18–20). In- and exclusion criteria are listed below:

Inclusion criteria

- Signed informed consent before any study specific procedures
- Able to read and understand Danish
- Age between 18 and 85 years
- The researcher believes that the participant understands what the study entails, is capable of following instructions, can attend when needed, and is expected to complete the study
- For fertile female participants: negative pregnancy test and use contraception during the study period.
- Within the current hospital admission and prior to inclusion, the patient must fulfill at least two of the following criteria to establish a diagnosis of AP (according to the revised Atlanta criteria (21): i) abdominal pain consistent with AP (acute onset of a persistent, severe, epigastric pain often radiating to the back); ii) serum amylase activity at least three times greater than the upper limit of normal; and iii) characteristic findings of AP on diagnostic imaging
- Predicted moderate or severe disease based on the fulfillment of 2 or more SIRS criteria

Exclusion criteria

- Definitive chronic pancreatitis according to the M-ANNHEIM criteria

- Known allergy towards study medication
- Known or suspected major stenosis obstruction or perforation of the intestines
- Toxic megacolon
- Known or suspected abdominal cancer (incl. intestine, pancreas and the biliary tree)
- Pre-existing renal insufficiency (defined as habitual estimated glomerular filtration rate (eGFR) below 45 ml/min/1,73m²)
- End-stage renal impairment requiring dialysis prior to inclusion
- Severe pre-existing comorbidities (assessed by investigator upon inclusion)
- Severe non-pancreaticobiliary infections or sepsis caused by non-pancreaticobiliary disease
- Child-Pugh class B or C liver cirrhosis
- Lactating

5. Data handling

Outcome	Source	Data collection rate	Datatype
PASS-score	From the patients' medical records (vital signs, lab results, quantification of need for opioid treatment), self-reported pain intensity and self-reported tolerance to solid foods	Daily during treatment and at 14-day follow-up	Ratio
Disease severity	Stratified as mild/moderate/severe using information about complications and organ failure from medical files	At 14-day follow-up	Ordinal
Subjective measures of pain intensity	Questionnaire: Pain intensity (current + worst/least pain the past 24 hours using NRS), pain interference score (7 parameters, scores 0-10)	Daily during treatment and at 14-day follow-up	Ordinal
Length of admission	Medical records, no. of days	90 days after randomization	Ratio
Mortality	Medical records; deceased y/n	90 days after randomization	Nominal
Circulating levels of pro- and anti-inflammatory cytokines,	Blood samples	Daily during treatment and at 14-day follow-up	Ratio
Intestinal permeability, gut transit time	Urine samples, CT-scans	Once during treatment (day 2-3)	Ratio
Prevalence of pancreatic complications	Stratified according to the revised Atlanta criteria (21) based on CT-scan	On day 5	Ordinal

Table 1

Delegated trial personnel at each trial center will register the collected data in the electronic case report form (eCRF) using the electronic data capture tool REDCap (Research Electronic Data Capture, version 10.6.26) hosted by the organization of The North Denmark Region. REDCap is a secure browser-based software, which meets all regulatory safety requirements (22,23). Data recording will begin when a participant is included and will occur gradually to the end of the trial. A detailed record of any corrections will be kept within REDCap. REDCap also contains features to improve data validation in the form of predefined variable ranges, options to detect that dates are in correct order and warnings if the forms are not sufficiently filled in.

All forms are filled out during (or immediately after) the assessment of a patient. It is possible to export validated data from REDCap to a statistical program (e.g. STATA, R) for further statistical analysis. When data have been entered, reviewed, and verified the data will be locked to prevent editing. Digitalized data are backed up and stored on specific drives at each site under the responsibility of the principal investigators for a minimum of 5 years after the study has ended.

6. Statistical Analysis

For the statistical analysis, the threshold for defining statistical significance will be 0.05. Values will be presented as mean and standard deviation or median and interquartile range depending on normality assessed by the Shapiro-Wilk test. When the data is qualitative, they will be presented as n (%).

6.1. Primary analysis

For the primary analysis of PASS, a repeated measures linear mixed-effects model will be used, and terms for the treatment group, assessment time point, and the interaction of treatment with assessment time point will be included. Baseline PASS scores will be added to the analysis as covariates. In case of statistical significance, a post-hoc Bonferroni corrected t-test will be employed to assess the difference in PASS scores between the groups at 48 hours, assuming normality is also confirmed using the Shapiro-Wilk test. If normality cannot be confirmed, the Mann-Whitney U-test will be used. The difference in PASS scores between the groups 48 hours after randomization is considered the primary efficacy parameter.

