2.5.2. Secondary Endpoints

The secondary and exploratory endpoints are assessed at baseline, daily during treatment and at 14-day follow-up.

3. Study Design

This is a multicenter, investigator-initiated, double-blind, 1:1 randomized, placebo-controlled interventional, parallel-group, superiority trial, that will be conducted at four referral centers for acute pancreatitis in Denmark (Aalborg University Hospital, Odense University Hospital, Copenhagen University Hospital Hvidovre, and Bispebjerg Hospital). The Danish regulations have approved the trial: The North Denmark Region Committee on Health Research Ethics (Identifier: N-20200060) and the Danish Medicines Agency (EudraCT identifier: 2020-002313-18). We plan to prospectively include 90 patients admitted with predicted moderate-to-severe acute pancreatitis. Written informed consent will be obtained from all participants prior to any trial-specific procedures. Patients entering the study, will be randomized 1:1 to receive 5 days of intravenous methylnaltrexone or matching placebo, during admission. While participating in the study, patients will receive standard treatment according to guidelines and no concomitant medication is prohibited. After discharge patients will be invited to complete a 14-day follow. In addition to treatment with PAMORA, patients will undergo a series of examinations daily during treatment and at the 14-day follow-up, according to figure 2.

[figure not shown]

Figure 2

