6.2. Secondary and exploratory analyses

Secondary and exploratory outcomes will be presented graphically to illustrate trends and potential differences between groups. Thus, outcomes measured repeatedly (PASS-score and levels of pro- and anti-inflammatory cytokines) will be illustrated using trend curves for each treatment group with single time points represented as mean and standard deviation or median and interquartile range, depending on normality. Single time point outcomes will be presented using boxplots depicting the difference between mean and standard deviation or median and interquartile range, depending on normality. Statistical analysis will also be performed for these outcomes according to below.

Repeated measures (e.g. daily PASS-scores, levels of pro- and anti-inflammatory cytokines, subjective measures of pain intensity)

For analysis of repeatedly measured secondary outcomes (daily PASS-scores, daily levels of pro- and anti-inflammatory cytokines), a repeated measures linear mixed-effects model will be used, as described for the primary endpoint. Furthermore, summary statistics and trend curves of PASS scores will be provided for the individual time points.

Single time point outcomes (length of admission, intestinal permeability and gut transit time)

Single time point outcomes (length of admission, measures of gut permeability and transit time) will be compared between groups using the two-sample unpaired t-test, when normality can be confirmed using the Shapiro-Wilk test, or the non-parametric analysis Mann-Whitney U-test when normality cannot be confirmed.

Counted data (disease severity, mortality)

After each patient has been placed in one of three categories (mild/moderate/severe), we will assess whether the prevalence of ‘moderate-to-severe’ disease is different between the two treatment groups. Thus, a 2 x 2 contingency table will be calculated (‘experienced event’ (D) being moderate or severe disease, ‘did not experience event’ (H) being mild disease and the χ^2 test will be employed to test the null hypothesis of no difference between groups.

Mortality between groups (assessed 90 days after randomization) will be analyzed using a 2 x 2 contingency table (‘experienced event’ (D) being death, ‘did not experience event’ (H) being survival). As we expect few of our patients to die during the study period, we plan to use Fishers exact test to test the null hypothesis of no difference between groups.

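### SAP 6.1 lets a normality test decide whether the primary 48-hour PASS result is a mean or a rank comparison, without tying it to the baseline-adjusted model

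*SAP*

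**What the plan says.** SAP 6.1 specifies a repeated-measures mixed model with treatment, time point and their interaction, and says "Baseline PASS scores will be added to the analysis as covariates". If that model is significant (the term is not named), a post-hoc Bonferroni-corrected t-test compares the groups at 48 hours, provided Shapiro-Wilk confirms normality. Otherwise: "If normality cannot be confirmed, the Mann-Whitney U-test will be used". The same paragraph makes the 48-hour difference the primary efficacy parameter. It attaches no covariate to either 48-hour test. It does not say whether Shapiro-Wilk is applied to each arm, to pooled scores or to residuals.

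SAP 3.1 sizes the trial "to detect a difference in the PASS score of 25 points with a within-group standard deviation of 40 points", which is a comparison of two means.

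Protocol 9.3 names only the mixed model for the primary analysis, with the 48-hour difference as the primary parameter. Its choice between a t-test and a non-parametric test is for outcomes measured at a single time point, not for PASS. SAP 6.2 has a similar rule for single-time-point outcomes: an unpaired two-sample t-test, "or the non-parametric analysis Mann-Whitney U-test when normality cannot be confirmed".

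**The concern.** Two things follow from the sequence in SAP 6.1.

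First, the covariate is in the model, but the number that decides the trial comes from a later test. Mann-Whitney takes no covariate, so in that branch baseline PASS cannot affect the 48-hour result. In the t-test branch the wording permits a contrast from the fitted model. But a t-test that gives way to Mann-Whitney on a Shapiro-Wilk result, with a matching rule for unpaired tests in 6.2, most naturally reads as a test on raw scores.

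Second, the nature of the primary result is not fixed in advance. A t-test addresses a mean difference in PASS points. Mann-Whitney addresses rank ordering, and by itself gives no mean difference to set against the 25 points in the sample size. PASS adds 100 points per failed organ system and 5 per mg of intravenous morphine equivalent, so a few patients can create a long right tail and trip the normality test.

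At stake are a clearly defined primary quantity and the precision available from a baseline score that is already collected.

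**Working it through.** **Plan's own figure.** Inputs from SAP 3.1: difference 25, SD 40, two-sided alpha 0.05, power 80%. n per group = 2 × (1.960 + 0.842)² × 40² / 25² = 40.19, rounded up to 41, as stated. (The t-based version gives 41.17, rounded up to 42.) The calculation has no baseline adjustment.

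**Precision with and without baseline, normal scores.** Inputs: 45 per arm (SAP 3.1) and a baseline-to-48-hour correlation r. The documents do not give r, so a range is assumed. Adjusted SD = 40 × √(1 − r²). Half-width of the 95% CI = 1.987 × SD × √(2/45). Power is from the two-sample t-test at 0.05, ignoring the model gate and any Bonferroni penalty.

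| r | SD | Power | Half-width (points) |
|---|---|---|---|
| unadjusted | 40.0 | 0.835 | 16.8 |
| 0.3 | 38.2 | 0.867 | 16.0 |
| 0.5 | 34.6 | 0.923 | 14.5 |
| 0.6 | 32.0 | 0.956 | 13.4 |

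The gain is about 3, 9 and 12 percentage points of power. At 41 per arm (normal approximation) the pattern is the same: 81% unadjusted against 84% at r = 0.3 and 90% at r = 0.5.

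**How often the switch fires.** This was simulated with 45 per arm, counting a trial if Shapiro-Wilk rejects at 0.05 in at least one arm. Both the per-arm use and the 0.05 level are assumptions. Scores are N(80, 35), plus 100 points for a fraction p with one organ failure; these inputs are assumed too. The implied total SD is √(35² + 100² × p(1 − p)), which is 41 at p = 5% and 46 at p = 10%; the plan assumes 40.

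- Truly normal scores: about 10% of trials go to Mann-Whitney.
- p = 5%: about 51%.
- p = 10%: about 68%.

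**Power when the switch is active.** The two results above rest on different data, so they were combined: the same contaminated scores, a 25-point shift, r = 0.3 in the normal part, gate and Bonferroni ignored.

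| Scenario | SAP selection rule | Baseline-adjusted (ANCOVA) |
|---|---|---|
| p = 5%, organ failure unrelated to baseline | 0.84 | 0.83 |
| p = 10%, organ failure unrelated to baseline | 0.78 | 0.75 |
| p = 5%, organ failure mostly present at baseline | 0.85 | 0.88 |
| p = 10%, organ failure mostly present at baseline | 0.77 | 0.84 |

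The change from adopting the adjusted contrast thus runs from −3 to +7 points at r = 0.3. Under no treatment effect, the selection rule rejected in about 5% of simulated trials.

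**The case against.** The strongest reply has four parts.

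1. *The t-test may already be a model contrast.* SAP 6.1 never says that it uses raw scores. A post-hoc Bonferroni-corrected t-test is common wording for a pairwise contrast after a mixed model, Shapiro-Wilk can be run on residuals, and the word unpaired appears only in 6.2. This stands in part: for the t-test branch the charge is a likely reading and an ambiguity, not a certainty. It does not rescue the Mann-Whitney branch.

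2. *Baseline PASS is not discarded.* A reader might infer that the covariate plays no role. It does: it is in the model that must be significant before the 48-hour test is reached. It is missing only from the deciding comparison, certainly in one branch and probably in the other.

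3. *No harm to validity or to the planned power.* A reader might infer that choosing the test from the data inflates false positives or leaves the trial underpowered. Neither is supported. The simulated error rate of the rule stayed near 0.05, the rule is pre-specified, and randomization protects against systematic bias. Before any Bonferroni penalty, unadjusted power at 45 per arm is 0.835, above the 80% target.

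4. *Mann-Whitney copes better with outliers.* On contaminated scores it beats the plain t-test, and where baseline predicts weakly the adjusted contrast can fall slightly below the SAP rule. This stands, which is why the gain in precision is usual rather than guaranteed.

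None of this answers the point that the plan cannot say in advance which quantity it will report.

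**Conclusion.** The point holds as a should-fix. Its firmest part needs no assumption: SAP 6.1 leaves the primary result as either a mean difference or a rank comparison, depending on a preliminary test of the outcome data, while the sample size is built on a mean difference and protocol 9.3 names only the mixed model.

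The precision part is conditional. With normal scores and correlations of 0.3 to 0.6, adjustment adds about 3 to 12 points of power and narrows the interval by 0.8 to 3.4 points on each side. With organ-failure outliers the effect on power depends on whether organ failure is already present at baseline. The correlation, the organ-failure rate and the shape of the score distribution are all assumptions.

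It would be tempting to apply the same conclusion to the test selection in SAP 6.2. Nothing here supports that: those outcomes, such as length of admission, were not examined, and the trial is not sized on them.

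**What to change.** In SAP 6.1, define the primary result as the treatment difference at 48 hours estimated from the mixed model, with post-baseline PASS as the response, time as a categorical factor, and baseline PASS and its interaction with time as covariates. Report it in PASS points with a 95% CI and p-value. This agrees with protocol 9.3.

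Delete the Shapiro-Wilk switch for the primary endpoint. To guard against skewness, specify beforehand a robust or bootstrap standard error for the same contrast, so that the quantity reported does not change. Keep Mann-Whitney at 48 hours as a named sensitivity analysis. Leave SAP 6.2 as it is on this point.

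The cost is SAP wording only, made before unblinding, with no new data. The sentence to be replaced also carries the significance gate and the Bonferroni correction. Those are separate questions, but the new text should be drafted with them in view. The downside is that the headline remains a mean difference even if scores are skewed, and a few points of power could be lost if baseline PASS turns out to predict the 48-hour score only weakly.

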6.2. Secondary and exploratory analyses

Secondary and exploratory outcomes will be presented graphically to illustrate trends and potential differences between groups. Thus, outcomes measured repeatedly (PASS-score and levels of pro- and anti-inflammatory cytokines) will be illustrated using trend curves for each treatment group with single time points represented as mean and standard deviation or median and interquartile range, depending on normality. Single time point outcomes will be presented using boxplots depicting the difference between mean and standard deviation or median and interquartile range, depending on normality. Statistical analysis will also be performed for these outcomes according to below.

Repeated measures (e.g. daily PASS-scores, levels of pro- and anti-inflammatory cytokines, subjective measures of pain intensity)

For analysis of repeatedly measured secondary outcomes (daily PASS-scores, daily levels of pro- and anti-inflammatory cytokines), a repeated measures linear mixed-effects model will be used, as described for the primary endpoint. Furthermore, summary statistics and trend curves of PASS scores will be provided for the individual time points.

Single time point outcomes (length of admission, intestinal permeability and gut transit time)

Single time point outcomes (length of admission, measures of gut permeability and transit time) will be compared between groups using the two-sample unpaired t-test, when normality can be confirmed using the Shapiro-Wilk test, or the non-parametric analysis Mann-Whitney U-test when normality cannot be confirmed.

Counted data (disease severity, mortality)

After each patient has been placed in one of three categories (mild/moderate/severe), we will assess whether the prevalence of ‘moderate-to-severe’ disease is different between the two treatment groups. Thus, a 2 x 2 contingency table will be calculated (‘experienced event’ (D) being moderate or severe disease, ‘did not experience event’ (H) being mild disease and the χ^2 test will be employed to test the null hypothesis of no difference between groups.

Mortality between groups (assessed 90 days after randomization) will be analyzed using a 2 x 2 contingency table (‘experienced event’ (D) being death, ‘did not experience event’ (H) being survival). As we expect few of our patients to die during the study period, we plan to use Fishers exact test to test the null hypothesis of no difference between groups.

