## 6. Introduction

### 6.1. Background and rationale

Acute pancreatitis (AP) has an annual incidence rate of approximately 35 pr. 100.000 person years in Denmark and has become one of the most frequent gastrointestinal discharge diagnoses (1). AP is associated with an overall complication rate of about 20%, and despite improved treatment the mortality is still near 3%. Unfortunately, no targeted pharmacologic treatment exists, to effectively alter the disease course, and the initial management of AP is currently based on supportive therapy with intravenous fluid resuscitation and analgesics. In the later stages, treatment is directed against complications such as mono- or multiorgan failure and infections, especially infected pancreatic necrosis (2).

The early phase of AP is characterised by a localized pancreatic inflammatory process, which can progress to a systemic inflammatory response syndrome (SIRS), which may be associated with multiorgan dysfunction - and failure (3). In turn, a compensatory anti-inflammatory response, whereby the inflammation becomes controlled, counterbalances the inflammatory process. However, in some cases an inadequate control of this counterbalance may lead to further organ dysfunction, immune paresis and late complications - in particular infections.

Pain is the cardinal symptom of AP and induces release of endogenous opioids, which is further potentiated by exogenous administered opioids used for pain management (4). The increased opioid exposure leads to a number of harmful effects on the gastrointestinal organs and the immune system (see figure 1). This may further promote the inflammatory response and worsen the course of the disease (5).

[figure not shown]

Figure 1: The effects of opioids on the gastrointestinal organs and the immune system

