2.2. Secondary Objectives and Outcomes

The secondary objective is to document the effects of methylnaltrexone treatment on several clinical outcomes in patients with acute pancreatitis.

The secondary outcomes are listed below:

- Difference between treatment groups (methylnaltrexone or placebo) in daily PASS-scores during treatment and at 14-day follow-up
- Difference between treatment groups on disease severity assessed using the revised Atlanta criteria (10), where patients are put into one of three categories (mild/moderate/severe)
- Difference between treatment groups on subjective measures of pain intensity and gastrointestinal function assessed using validated questionnaires (13–15) daily during treatment and at 14-day follow-up
- Difference between treatment groups in length of admission and mortality, assessed retrospectively 90 days after admission, using the patients' medical records

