2.5. Specification of endpoints

The primary outcome at the primary endpoint will be analyzed by intention-to-treat (ITT), whereas the secondary endpoints will be per-protocol (PP) analyses. Several factors such as treatment effect of methylnaltrexone and possible side-effects (17) may lead to an uneven distribution between excluded patients in the treatment groups (e.g. if methylnaltrexone patients are discharged earlier or discontinue treatment due to side effects). The ITT-analysis will protect against the potential bias of excluding patients unevenly according to which treatment they received. Only if the participant is randomized but never receives treatment, will they be excluded from the ITT-analysis.

The PP-analysis aims to uncover the treatment effect under ideal conditions in terms of treatment duration and follow-up. Furthermore, the PP-analysis is expected to provide mechanistic insights into the role of opioids and opioid antagonism in acute pancreatitis. Participants are included in the PP-analysis, when:

1. > 75 % of the study drug has been given
2. No major protocol deviations have been recorded

The trial is designed as a superiority trial, and we expect to see an effect of treatment after 48 hours of treatment – which is the explanation for choice of primary endpoint. Thus, we expect that the group allocated to the methylnaltrexone treatment, compared to the usual care group, will have:

1. Reduced disease severity (lower PASS-scores, lower prevalence of severe disease)
2. Improved clinical outcomes (lower pain scores, shorter admission lengths, reduced mortality, inflammatory cytokines/intestinal permeability/transit times closer to normal range, reduced prevalence of pancreatic complications)

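### The length-of-admission comparison has no rule for in-hospital deaths, so an early death is scored like an early discharge; the effect is small at the documents' own mortality

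*SAP*

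**What the plan says.** Length of admission is a secondary outcome, listed with mortality in SAP 2.2: "Difference between treatment groups in length of admission and mortality, assessed retrospectively 90 days after admission". Table 1 in SAP section 5 records it as "Medical records, no. of days" and gives the time as 90 days after randomization, so the two places start the 90-day clock differently.

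On the analysis, SAP 6.2 says: "Single time point outcomes (length of admission, measures of gut permeability and transit time) will be compared between groups". The test is the unpaired t-test, or Mann-Whitney when the Shapiro-Wilk test does not confirm normality. SAP 2.5 gives the direction of benefit: "Improved clinical outcomes (lower pain scores, shorter admission lengths, reduced mortality".

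The analysis set also comes from SAP 2.5: "whereas the secondary endpoints will be per-protocol (PP) analyses". Entry to that set requires that "> 75 % of the study drug has been given", with no major protocol deviation.

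Mortality is tested separately at 90 days by Fisher's exact test, with few deaths expected. The last-observation-carried-forward rule in SAP 6.3 covers early discharge and missing values. Neither says what value a patient who dies in hospital contributes to length of admission, or what is done with a patient still admitted at day 90.

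**The concern.** A stay can end in recovery or in death, and a count of days does not tell them apart. Suppose one patient dies on day 5 and another goes home well on day 5. Both contribute 5 days, and since shorter is read as better, the death counts in favour of its arm.

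The SAP expects methylnaltrexone to shorten stays and to reduce deaths. If early deaths fall mainly on placebo, raw days shorten the placebo stay and set these two expected effects against each other. If early deaths fall mainly on the active drug, the comparison makes the drug look better. The trial enrols predicted moderate or severe disease, so at least one death is likely and the analyst will have to choose a rule. It should be fixed before unblinding.

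**Working it through.** **The plan's own figure.** The only sample-size figure is for the primary PASS endpoint (SAP 3.1: difference 25, SD 40, 80% power, two-sided 0.05). n = 2 x (1.96 + 0.842)^2 x 40^2 / 25^2 = 40.2, rounded up to 41 per group, as stated. There is no figure for length of admission.

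**Expected deaths.** Protocol 6.1 says that "despite improved treatment the mortality is still near 3" per cent, for acute pancreatitis overall. No rate is given for the enrolled group.
- Expected deaths: 90 x 0.03 = 2.7.
- Chance of at least one: 1 - 0.97^90 = 94%.

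**Per-protocol entry.** 75% of 5 days is 3.75 days of infusion. Deaths before that point leave the per-protocol set; later deaths stay in as raw days.

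**Simulation.** 45 per arm, Mann-Whitney, two-sided 0.05. The following inputs are assumptions, not in the documents: lognormal stays with medians 8 (placebo) and 5.8 days (active), log-SD 0.7, and the death rates and death days shown. The last column ranks deaths worst and keeps all patients. Where early deaths are removed, those before day 3.75 are dropped from the raw-days analysis only.

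| Deaths, placebo v active | Death days | Set for raw days | Power, raw days | Power, deaths worst |
|---|---|---|---|---|
| 3% v 3% | 2-7 | all patients | 54% | 51% |
| 3% v 1.5% | 2-7 | all patients | 52% | 57% |
| 3% v 1.5% | 2-30 | all patients | 56% | 57% |
| 7% v 0% | 2-7 | all patients | 43% | 73% |
| 7% v 0% | 2-7 | early deaths removed | about 48% | about 70% |
| 7% v 0% | 2-30 | early deaths removed | about 65% | about 72% |
| 10% v 2% | 2-7 | all patients | 40% | 72% |
| 10% v 2% | 2-7 | early deaths removed | 47% | 73% |

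Repeat runs differ by one or two points.

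**At the documents' rate, per-protocol set.** A second simulation took a stay 30% shorter on active and deaths at 3% v 1.5%. With deaths on days 1-7, power is 62.9% with raw days and 66.0% with deaths ranked worst, a loss of 3.1 points. With deaths on days 1-30 it is 64.4% and 65.2%, a loss of 0.8. Allowing for simulation error and the choice of window, the loss is about 1 to 4 points. If all patients are kept and deaths are early, it is 59.3% against 64.3%, or 5 points.

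**Harm direction.** Assume no effect on stay, deaths on days 2-7 at 3% on placebo and 10% on active, and all patients kept. Raw days then give a significant result favouring the drug in 5.0% of trials, against 2.5% by chance and 0.6% with deaths ranked worst.

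**Limit of the per-protocol rows.** They remove early deaths but not early discharges. With the assumed stays, and infusion from admission, the share leaving hospital before day 3.75 is Phi(ln(3.75/5.8)/0.7) = 27% on active and Phi(ln(3.75/8)/0.7) = 14% on placebo. The true per-protocol comparison would therefore be selected further, by an amount that the documents do not let one compute.

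**The case against.** The strongest reply is that the problem is small and partly pre-empted. Few deaths are expected, and mortality is reported beside the stay result, so an imbalance would be visible. The per-protocol rule removes some of the earliest deaths, and SAP 3.2 replaces patients with less than 48 hours of treatment. A later death can carry a long stay, and Protocol 6.1 itself describes late complications. If both arms truly had 3% mortality, a split of at least 3 v 0 against placebo would have only about a 4% chance.

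Most of this stands, and it limits the size. It does not remove the point. Dropping early deaths is itself selection after randomization. Separate reporting shows the deaths but does not correct the stay comparison, and Fisher's test gives p = 0.24 at 3 v 0 of 45 and needs 6 v 0 to fall below 0.05.

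Three stronger readings are tempting, and the documents do not support them.
- *Raw days can reverse a benefit.* No simulated scenario with a shorter stay produced more than a negligible share of significant results in the wrong direction. The estimate turns only when the benefit is on mortality alone and deaths are early. In the per-protocol set, the chance that a treated patient stays longer than a control is then 0.503 at 3% v 0%, where 0.5 means no difference. It is 0.494, the right direction, if deaths spread over days 1-30. Significant wrong-direction results become material only at mortality such as 20% v 5%: 5.0% of trials in the per-protocol set, against 2.5% by chance.
- *The plan loses 30 points of power.* The 43% v 73% and 40% v 72% gaps keep every patient in the raw-days analysis, which the SAP does not do, and need an unbalanced split with all deaths in the first week.
- *Counting from admission biases the result.* Days before randomization are balanced in expectation by randomization. They add noise, not bias.

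**Conclusion.** The point holds in a limited form. SAP 6.2 compares raw days, shorter is read as benefit, and nothing distinguishes a stay ended by death from a discharge. The result can be diluted, or flattered if early deaths are commoner on active drug.

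At the only mortality figure in the documents, the cost in the per-protocol set is about 1 to 4 power points. It reaches roughly 20 points (48% v 70%) only under assumed early deaths split 7% v 0%, and falls to about 7 points (65% v 72%) when those deaths spread over days 2-30. The split, the timing and the stay distribution are all assumptions; the absence of a rule is not. This is a minor but worthwhile correction to one secondary outcome.

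**What to change.** In SAP 6.2, take length of stay out of the general single-time-point rule and specify:
- stay counted from randomization to day 90, in all treated patients rather than the per-protocol set;
- a Mann-Whitney comparison with in-hospital deaths given the worst rank, and patients still admitted at day 90 ranked just below them;
- stay among survivors reported descriptively.

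Days alive and out of hospital to day 90 is an acceptable alternative. Reconcile the 90-day clock, which runs from admission in SAP 2.2 and Protocol 9.1.2 but from randomization in SAP Table 1 and the mortality analysis in SAP 6.2.

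The cost is a few sentences before unblinding. Stay and death are already taken from medical records, but SAP 6.3 stops all data collection for patients discharged with under 48 hours of treatment, so the SAP must say whether these two items are still extracted for them. The result is no longer a plain difference in mean days and becomes a composite with mortality. If mortality is equal in the arms, worst ranking costs a little power (54% to 51% at 3% v 3%). The primary endpoint and sample size do not change.
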